4.2.5 Objective Response Rate (Investigator-assessed)

Investigator-assessed ORR is defined similarly as described for the primary endpoint above (Section 4.1) and will be further characterized by TTR and DOR.

First subsequent therapy date per Investigator is defined as the earliest start date on or after the first study therapy date among systemic anti-cancer therapy, stem cell transplant, non-palliative radiotherapy and local tumor treatment (non-palliative radiotherapy or other).

4.3 Exploratory Endpoints

[REDACTED]

[REDACTED]

[REDACTED]

[REDACTED]

[REDACTED]

4.3.7 Outcome Research

4.3.7.1 EORTC-QLQ-C30

Health-related quality of life (HRQoL) will be assessed using the European Organization for Research and Treatment of Cancer (EORTC) QLQ-C30 questionnaire Version 3. It is a 30-item instrument that has gained wide acceptance in oncology clinical studies. The EORTC QLQ-C30 is composed of multi-item and single scales. These include five functional scales (physical, role, emotional, social, and cognitive), three symptom (fatigue, nausea and vomiting, and pain) and a global health status/QoL scale and six single items (dyspnea, insomnia, appetite loss, constipation, diarrhea and financial difficulties). All scales and single items meet the standards for reliability. The reliability and validity of the questionnaire is highly consistent across different language-cultural groups³⁰. Except for the overall health status and global quality of life items, responses for all items are 4 point categorical scales ranging from 1 (Not at all) to 4 (Very much). The overall health status/quality of life responses are 7-point Likert scales.

Data will be scored according to the algorithm described in the EORTC QLQ-C30 scoring manual, as follows:

Functional scales:

- Physical functioning: $(1 - ((Q1+Q2+Q3+Q4+Q5)/5 - 1)/3) * 100$
- Role functioning: $(1 - ((Q6+Q7)/2 - 1)/3) * 100$
- Emotional functioning: $(1 - ((Q21+Q22+Q23+Q24)/4 - 1)/3) * 100$
- Cognitive functioning: $(1 - ((Q20+Q25)/2 - 1)/3) * 100$
- Social functioning: $(1 - ((Q26+Q27)/2 - 1)/3) * 100$

Global health status:

- Global health status/QoL: $((Q29+Q30)/2 - 1)/6 * 100$

Symptom scales/items:

- Fatigue: $((Q10+Q12+Q18)/3 - 1)/3 * 100$
- Nausea and vomiting: $((Q14+Q15)/2 - 1)/3 * 100$
- Pain: $((Q9+Q19)/2 - 1)/3 * 100$

- Dyspnea: $((Q8-1)/3) * 100$
- Insomnia: $(Q11-1)/3 * 100$
- Appetite loss: $(Q13-1)/3 * 100$
- Constipation: $(Q16-1)/3 * 100$
- Diarrhea: $(Q17-1)/3 * 100$
- Financial difficulties: $(Q28-1)/3 * 100$

Missing values will be imputed for missing items by “assuming that the missing items have values equal to the average of those items which are present” for any scale in which at least half the items are completed. A scale in which less than half of the items are completed will be treated as missing. This is the method proposed in the scoring manual. A questionnaire will be considered as received if at least one of the 15 scales is non-missing (after imputation).

All questionnaires completed at baseline and on-study will be assigned to a time-point according to the windowing criteria in Table 4.3.7.1-1 and included in the analysis. In case a subject has two on-study assessments within the same window, the assessment closest to the time-point will be used. And, in the case of two assessments at a similar distance to the time-point, the latest one will be chosen. In the event where the subject has no assessment at all in a specific window, the observation will be treated as missing for that time-point.

Table 4.3.7.1-1: Time Windows for EORTC-QLQ-C30 Assessments

Nominal Time-Point	Time Window
Week 1 (Baseline)	Prior to first dose on Day 1
Week 9	Day 2 thru Day 85, inclusive
Every 8 weeks up to week 25	Nominal Day (+ 28 days / - 27 days, inclusive)
Week 33	Day 198 thru Day 267, inclusive
Every 12 weeks thereafter	Nominal Day (+ 42 days / - 41 days, inclusive)
Follow-up 1	NA
Follow-up 2	NA

4.3.7.2 EuroQoL EQ-5D

Subjects’ overall health status will be assessed using the EuroQol Group’s self-reported health status measure (EQ-5D-3L)³¹. EQ-5D essentially has 2 components- the EQ-5D descriptive system and the EQ visual analogue scale (EQ VAS).

The EQ-5D descriptive system comprises the following 5 dimensions: mobility, self-care, usual activities, pain/discomfort and anxiety/depression. Each dimension has 3 levels: no problems, some problems, severe problems. Once the data have been collected and a database created, a scoring function can be used to assign a value (i.e., EQ-5D index score) to self-reported health states from a set of population-based preference weights.

The EQ VAS records the subject’s self-rated health state on a 100-point vertical, visual analogue scale (0 = worst imaginable health state; 100 = best imaginable health state)³².

4.3.8 Biomarker Data

[Redacted content]

4.3.8.2 Other Biomarkers

[Redacted content]

5 SAMPLE SIZE AND POWER

The planned sample size for this study will be approximately 90 treated subjects. The sample size was determined based on two considerations: the ability to produce a CI which would exclude an ORR of 20%, which is not considered clinically relevant and provide sufficient information for a reliable understanding of the safety profile.

Assuming the true ORR is 35%, the study has approximately 87% power to reject the null hypothesis that the true ORR is $\leq 20\%$, considering a 2-sided alpha of 5%. In addition, [Table 5-1](#) summarizes the 95% exact CI for the target ORRs ranging from 30% to 44% with sample size of 90. At observed ORR $\geq 30\%$, the lower bound of the 95% CI excludes 20%.

Table 5-1: Observed ORR with Exact 95% CI

True ORR	95% Exact CI
30%	[20.8%-40.6%]
34%	[24.7%-45.2%]
40%	[29.8%-50.9%]
44%	[34.0%-55.3%]

6 STUDY PERIODS, TREATMENT REGIMENS AND POPULATIONS FOR ANALYSES

6.1 Study Periods

6.1.1 Baseline Period

Baseline evaluations or events will be defined as evaluations or events that occur before the date and time of the first dose of study treatment.

In cases where the time (onset time of event or evaluation time and dosing time) is missing or not collected, the following definitions will apply:

- Pre-treatment AEs will be defined as AEs with an onset date prior to but not including the day of the first dose of study treatment
- Baseline evaluations (laboratory tests, pulse oximetry and vital signs) will be defined as evaluations with a date on or prior to the day of first dose of study treatment

If there are multiple valid assessments, the assessment that is closest to day (and time if collected) of the first dose of study treatment will be used as the baseline in the analyses. If multiple

assessments are collected at the same date (and time if collected), the assessment with the latest database entry date (and time if collected) will be considered as baseline.

6.1.2 Post Baseline Period

On-treatment AEs will be defined as AEs with an onset date-time on or after the date-time of the first dose of study treatment (or with an onset date on or after the day of first dose of study treatment if time is not collected or is missing). An AE will be counted as on-treatment if the event occurred within 30 days (or 100 days depending on analysis) of the last dose of study treatment. Refer to Core SAP²⁹.

On-treatment evaluations (laboratory tests, pulse oximetry and vital signs) will be defined as evaluations taken after the day (and time, if collected and not missing) of first dose of study treatment. An evaluation will be counted as on-treatment if it occurred within 30 days (or 100 days depending on analysis) of the last dose of study treatment. Refer to Core SAP²⁹.

6.2 Treatment Regimens

All subjects will be treated with nivolumab.

6.3 Populations for Analyses

6.3.1 Analysis Populations

The following populations will be defined.

- **All enrolled subjects:** All subjects who signed an informed consent form and were registered into the IVRS.
- **All treated subjects:** All enrolled subjects who received at least one dose of nivolumab. This is the primary population for efficacy and safety.
- **All response evaluable subjects:** All treated subjects who have baseline and at least one on-study evaluable tumor measurement.
- **PK subjects:** All enrolled subjects with available serum time-concentration data from subjects dosed with nivolumab.
- **Immunogenicity evaluable subjects:** all treated subjects with baseline and at least one post baseline immunogenicity assessment.
- **All PD-L1 tested subjects:** All enrolled subjects who had a tumor tissue sample available for assessment of PD-L1 expression.
- **All PD-L1 evaluable subjects:** All treated subjects with quantifiable baseline PD-L1 expression
- **Biomarker subjects:** All treated subjects with available biomarker data.
- **Outcomes Research subjects:** all treated subjects who have an assessment at baseline (Visit 1 assessment prior to administration of drug) and at least 1 subsequent assessment (for EORTC QLQ-C30 and EQ-5D separately).

7 STATISTICAL ANALYSES

7.1 General Methods

Unless otherwise noted, the bulleted titles in the following subsections describe tabulations of discrete variables, by the frequency and proportion of subjects falling into each category. Percentages given in these tables will be rounded and, therefore, may not always sum to 100%. Continuous variables will be summarized using the mean, standard deviation, median, minimum and maximum values.

Time to event distribution (e.g. progression free survival, overall survival, time to response, and duration of response) will be estimated using Kaplan Meier techniques. Median survival time along with 95% CI will be constructed based on a log-log transformed CI for the survivor function $S(t)$ ^{33,34}. Rates at fixed time points will be derived from the Kaplan Meier estimate and corresponding confidence interval will be derived based on Greenwood formula³⁵ for variance derivation and on log-log transformation applied on the survivor function $S(t)$ ³⁶.

7.2 Study Conduct

7.2.1 Accrual

The following will be summarized on the enrolled population:

- Number of subjects accrued by country and investigational site
- Number of subjects accrued by month

A by subject listing of accrual will be produced.

7.2.2 Relevant Protocol Deviations

The following programmable deviations will be considered as relevant protocol deviations. Non-programmable relevant eligibility and on-treatment protocol deviations, as well as significant (both programmable and non-programmable) eligibility and on-treatment protocol deviations will be reported through ClinSIGHT listings.

At entrance:

- Subjects without documented relapsed or refractory FL.
- Subjects without treatment of FL consisting of ≥ 2 prior treatment lines; each of the two prior treatment lines must include a CD20 and/or an alkylating agent (e.g., bendamustine, cyclophosphamide, ifosfamide, chlorambucil, melphalan, busulfan, nitrosoureas). At least one of the prior treatment lines must include rituximab.
- Subject without measurable disease at baseline.
- Subject with baseline ECOG not in (0, 1).

On-Study:

- Any concurrent antineoplastic therapy (i.e., chemotherapy, hormonal therapy, immunotherapy, radiation therapy except for palliative radiation therapy, or standard or investigational agents for treatment of cancer).

A by subject listing will be produced.

7.3 Study Population

7.3.1 Subject Disposition

The total number of subjects enrolled (treated or not) will be presented along with the reason for not being treated.

Number of subjects who discontinued treatment along with corresponding reason will also be tabulated.

7.3.2 Demographics and Other Baseline Characteristics

Descriptive statistics will be summarized the following baseline characteristics for all treated subjects. All baseline presentations will identify subjects with missing measurements. Listings will also be provided.

- Age (descriptive statistics)
- Age categories (< 65, ≥ 65 and < 75, ≥ 75)
- Gender, Race/Ethnicity
- Region (US/Canada vs. Europe vs. Rest of World)
- ECOG PS (0, 1, >1, Not Reported)
- weight
- Smoking Status (current/former vs never smoker vs. unknown)
- Time from initial disease diagnosis to first dose of nivolumab (descriptive statistics and (< 1 year, 1 - < 2 year, 2 - < 3 year, 3 - < 5 year, 5 - < 7 year, 7 - < 10 year, ≥ 10 years)
- Disease stage at initial diagnosis (Stage I-II-III-IV)
- Follicular lymphoma international prognostic index (FLIPI) Score (0, 1, 2, 3, 4, 5) at initial diagnosis
- Lymphoma involvement in bone marrow at baseline (Yes/No/Not Reported)
- Disease status at study entry (Relapse, Refractory)
- All lesions (Investigator Tumor Assessments at Baseline): sites of diseases, number of disease sites per subject
- Target Lesions (Investigator Tumor Assessments at Baseline): Presence of target lesions, site of target lesion, sum of diameters of target lesions.

7.3.3 Medical History

General medical history will be listed by subject and pretreatment events will be tabulated.

7.3.4 Prior therapy

The following will be summarized:

- Number of subjects by type of prior therapy received:
 - Immunotherapy by Monoclonal Antibodies
 - Steroid
 - Chemotherapy – Anthracyclines
 - Chemotherapy – Other than Anthracyclines
 - Kinase Inhibitors
 - Immunomodulatory Derivatives
 - Radioimmunotherapy
 - Other
- Number of subjects per type of regimen for first line of therapy (e.g. R-CHOP vs R-CVP vs OTHER)
- Number of prior systemic cancer therapy lines received (0, 1, 2, 3, 4, ≥ 5)
- Best response to most recent prior systemic cancer therapy (CR vs. PR vs. SD vs. Relapse/PD vs. Unable to Determine vs. Not Applicable vs. Not Reported) (Note: Not Applicable is used when the agent is a conditioning regimen for stem cell transplant)
- Time from completion of most recent prior regimen to treatment (< 3, 3 - 6, > 6 months)
- Prior radiotherapy (yes, no)
- Prior autologous transplant (yes, no)

Other Prior therapy:

- Prior/current non-study medication classified by anatomic and therapeutic classes.

Medication will be reported using the generic name. A listing by subject will also be provided.

7.3.5 Baseline Examinations

Percentage of subjects with abnormal baseline physical examination will be tabulated by examination criteria.

7.4 Extent of Exposure

Analyses in this section will be performed in all treated subjects.

7.4.1 Administration of Study Therapy

The following parameters will be summarized (descriptive statistics):

- Relative dose intensity (%) using the following categories: < 50%; 50 - < 70%; 70 - < 90%; 90 - < 110%; ≥ 110%.
- Number of doses received (summary statistics)
- Cumulative dose
- Duration of treatment: duration of treatment will be presented using a Kaplan-Meier curve whereby the last dose date will be the event date for subjects who discontinued study therapy. Subjects who are still on study therapy will be censored on their last dose date. Median duration of treatment and associated 95% CI will be provided.
- A by-subject listing of dosing of study medication (record of study medication, infusion details, dose change) and a listing of batch number will be also provided.

Table 7.4.1-1: Administration of study therapy: definition of parameters

nivolumab	
Dosing schedule per protocol	3mg/kg every 2 weeks
Dose	Dose (mg/kg) is defined as Total Dose administered (mg)/Most recent weight (kg). Dose administered in mg at each dosing date and weight are collected on the CRF.
Cumulative Dose	Cum dose (mg/kg) is sum of the doses (mg/kg) administered to a subject during the treatment period.
Relative dose intensity (%)	$\text{Cum dose (mg/kg)} / [(\text{Last dose date} - \text{Start dose date} + 14) \times 3 / 14] \times 100$
Duration of treatment	Last dose date - Start dose date + 1

7.4.2 Modifications of Study Therapy

7.4.2.1 Dose delays

Treatment may be delayed for up to a maximum of 6 weeks from the last dose. A dose will be considered as actually delayed if the delay is exceeding 3 days (i.e., greater than or equal to 4 days from scheduled dosing date). Length of delay is defined as (duration of previous cycle in days - 14). Dose delays will be divided into following categories: 4 - < 8 days, 8 - < 15 days, 15 - < 42, ≥ 42 days. Reason for dose delay/omission will be retrieved from CRF dosing pages.

The following parameters will be summarized.

- Number of subjects with at least one dose delayed, number of dose delayed per subject, Length of Delay and Reason for Dose Delay

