### **Treatment:**

- Treatment begins with the call to the IVRS to obtain vial assignments. A negative pregnancy test should be documented within 24 hours prior to the start of investigational product. Subsequently, women of childbearing potential (WOCBP) must have a pregnancy test every 4 weeks ( $\pm$  7 days) regardless of dosing schedule.
- The subject should receive the dose of study medication within 1 day of vial assignment.
- Subjects may be dosed no less than 12 days between doses and no more than 3 days after the scheduled dosing date. Dose given after the 3-day window is considered a dose delay. A maximum delay of 42 days between doses is allowed.
- All of the vital signs starting after Cycle 1 will be collected within 72 hours prior to dosing.
- Adverse event assessments should be documented at each clinic visit.
- Biomarker, PK and immunogenicity samples will be done according to the schedules in [Sections 5.5, 5.6, and 5.8.1](#).
- Study drug is administered as an IV infusion over 60 minutes on Treatment Day 1 of each cycle until disease progression or discontinuation due to toxicity, withdrawal of study consent, or the study ends. Treatment beyond progression is allowed in certain instances as described in [Section 4.3.8](#)
- Study drug dosing may be delayed for toxicity. See [Section 4.3.2](#).
- Subjects will be evaluated for response according to revised International Working Group Criteria beginning at Week 9 and continuing every 8 weeks ( $\pm$  1 week) for the first eight months of treatment, then every 12 weeks ( $\pm$  2 weeks) up to 2 years of treatment, continuing every 6 months ( $\pm$  3 weeks) beyond 2 years of treatment, until disease progression is documented or until the subject initiates a preparative regimen for allogeneic SCT or ASCT, whichever occurs earlier. If the subject discontinues treatment prior to disease progression, tumor assessment will continue in the follow-up phase.
- Screening/Baseline and all subsequent scans will be submitted to an IRRC, once the subject has been enrolled and throughout the study period.
- Quality of Life (QoL) tools must be completed at Treatment Day 1 prior to the first dose of study drug. Following that, QoL tools will be completed according to the schedule in [Table 5.1-2](#) and [Table 5.1-3](#).
- This phase ends when the subject is discontinued from study therapy. For a complete list of reasons for treatment discontinuation, refer to [Sections 3.5](#) and [4.3.5](#).

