#### **4.3 Selection and Timing of Dose for Each Subject**

Eligible subjects will receive treatment with nivolumab at a dose of 3 mg/kg, as a 60-minute IV infusion, on Day 1 of a treatment cycle every 2 weeks. Subjects must be treated within one day after study drug vial assignment. Dosing calculations should be based on the body weight assessed as per [Table 5.1-2](#). If the subject's weight on the day of dosing differs by > 10% from the weight used to calculate the dose, the dose must be recalculated. All doses should be rounded to the nearest milligram. There will be no dose escalations or reductions of nivolumab allowed. Subjects may be dosed no less than 12 days between doses and no more than 3 days after the scheduled dosing date. There are no premedications recommended for nivolumab on the first cycle. If an acute infusion reaction is noted, subjects should be managed according to [Section 4.3.6](#).

Treatment may be delayed for up to a maximum of 6 weeks from the previous dose (See [Sections 4.3.2](#) and [4.3.4](#)).

Tumor assessments by spiral CT/MRI for all subjects should continue as per protocol even if dosing is delayed.

Subjects will be monitored continuously for AEs while on study. Treatment modifications (eg, dose delay or discontinuation) will be based on specific laboratory and adverse event criteria.

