#### **4.3.4 Criteria to Resume Nivolumab Dosing**

Subjects may resume treatment with nivolumab when the drug-related AE(s) resolve to Grade  $\leq$  1 or baseline value, with the following exceptions:

- Subjects may resume treatment in the presence of Grade 2 fatigue
- Subjects who have not experienced a Grade 3 drug-related skin AE may resume treatment in the presence of Grade 2 skin toxicity
- Subjects with baseline AST/ALT or total bilirubin in the Grade 1 toxicity range who require dose delays for reasons other than a 2-grade shift in AST/ALT or total bilirubin may resume treatment in the presence of Grade 2 AST/ALT OR total bilirubin
- Subjects with combined Grade 2 AST/ALT AND total bilirubin values meeting discontinuation parameters (Section 4.3.5) should have treatment permanently discontinued
- Drug-related pulmonary toxicity, diarrhea, or colitis must have resolved to baseline before treatment is resumed
- Drug-related endocrinopathies adequately controlled with only physiologic hormone replacement may resume treatment.

If the criterion to resume treatment is met, the subject should restart treatment at the next scheduled timepoint per protocol.

If treatment is delayed  $>$  6 weeks, the subject must be permanently discontinued from study therapy, except as specified in Section 4.3.5.

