- Any dosing interruption lasting > 6 weeks from the previous dose with the following exceptions:
  - Dosing interruptions to allow for prolonged steroid tapers to manage drug-related adverse events are allowed. Prior to re-initiating treatment in a subject with a dosing interruption lasting > 6 weeks, the BMS medical monitor must be consulted. Tumor assessments should continue as per protocol even if dosing is interrupted.
  - Dosing interruptions > 6 weeks that occur for non-drug-related reasons may be allowed if approved by the BMS medical monitor. Prior to re-initiating treatment in a subject with a dosing interruption lasting > 6 weeks, the BMS medical monitor must be consulted. Tumor assessments should continue as per protocol even if dosing is interrupted.
- Any adverse event, laboratory abnormality, or intercurrent illness which, in the judgment of the Investigator, presents a substantial clinical risk to the subject with continued nivolumab dosing.

- Disease progression (as determined by investigator assessment following the guidelines given in [Section 5.4](#)). Treatment beyond progression is allowed in certain instances as described in [Section 4.3.8](#).
- Subject who initiated the preparative regimen for allogeneic SCT or ASCT after the first dose of nivolumab treatment.

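### Does the 42-day top cut for dose delays in SAP 7.4.2.1 need re-cutting to match the 6-weeks-from-last-dose limit?

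*SAP*

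**What the plan says.** SAP 7.4.2.1 opens with the treatment limit: "Treatment may be delayed for up to a maximum of 6 weeks from the last dose". It counts a dose as delayed once it is at least 4 days past the scheduled date. It then gives the scale and introduces the bins: "Length of delay is defined as (duration of previous cycle in days - 14). Dose delays will be divided into following categories". There are four bins, in days of delay: 4 to under 8, 8 to under 15, and then "15 - < 42, ≥ 42 days". The summary reports the number of subjects with a delay, delays per subject, length of delay and reason.

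The protocol gives the limit in four places:

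- Section 3.1, Treatment: "A maximum delay of 42 days between doses is allowed".
- Section 4.3: "Treatment may be delayed for up to a maximum of 6 weeks from the previous dose".
- Section 4.3.5, as a discontinuation criterion: "Any dosing interruption lasting > 6 weeks from the previous dose with the following exceptions". The exceptions are prolonged steroid tapers for drug-related events, and non-drug-related reasons approved by the medical monitor.
- Section 4.3.4, for a delay over the limit: "6 weeks, the subject must be permanently discontinued from study therapy, except as specified in Section 4.3.5". For a subject who meets the resumption criteria it adds that "the subject should restart treatment at the next scheduled timepoint per protocol".

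**The concern.** The number 42 appears on two scales. The limit runs from one dose to the next. The bins run on delay, which is that gap less the 14-day cycle. A top bin starting at 42 looks as though it was meant to pick out gaps beyond the 6-week limit, but on the delay scale it starts two weeks later.

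Someone who reads the top bin as the over-6-weeks group would miss gaps of 43 to 55 days and undercount long interruptions. Exceeding 6 weeks leads to discontinuation unless an exception applies, so that count could interest a reader of the exposure section.

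**Working it through.** **Inputs.** The limit is 6 weeks from the last dose (SAP 7.4.2.1; Protocol 3.1, 4.3 and 4.3.5). The cycle is 14 days (SAP 2.1). Delay equals the duration of the previous cycle minus 14 (SAP 7.4.2.1). I take the duration of the previous cycle to be the number of days from one dose to the next.

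**Lower cut.** A delay of more than 3 days first occurs at 4 days, a gap of 4 + 14 = 18 days. The first bin starts at 4, so the lower cut agrees with the 3-day window.

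**Upper cut.** The limit is 6 × 7 = 42 days between doses, or 42 - 14 = 28 days of delay. The top bin starts at 42 days of delay, a gap of 42 + 14 = 56 days. The difference is 56 - 42 = 14 days, exactly one cycle.

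**Bins converted to gaps between doses (whole days).**

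| Delay (days) | Gap between doses (days) | Against the 42-day limit |
|---|---|---|
| 4 to 7 | 18 to 21 | all within |
| 8 to 14 | 22 to 28 | all within |
| 15 to 41 | 29 to 55 | 29 to 42 within; 43 to 55 beyond |
| 42 or more | 56 or more | all beyond |

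The third bin holds 41 - 15 + 1 = 27 possible whole-day values, 14 within the limit and 13 beyond. These are possible values, not patients.

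**How often the bin would mix.** This depends on where restarts fall.

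- Exactly on the 14-day grid, which is one reading of the restart rule in Protocol 4.3.4, gaps are 28, 42, 56 and 70 days. The delays are 14, 28, 42 and 56. The 42-day gap falls in the third bin and the 56-day gap in the top bin, so the cut separates them correctly. The share of over-limit gaps placed in the third bin is 0%.
- On the same grid with the dosing window of Protocol 3.1 (at least 12 days between doses, read here as up to 2 days early, and up to 3 days late), gaps of 43 to 45 days (42 + 1 to 42 + 3) and of 54 and 55 days (56 - 2 and 56 - 1) become possible. All of these fall in the third bin.
- If every over-limit gap lasted 43 to 55 days, the share would be 100%.

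The documents give no distribution of gaps, so the range stays at 0% to 100%.

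**What uses the bins.** Relative dose intensity (SAP 7.4.1) is computed from cumulative dose and the first and last dose dates. The efficacy endpoints (SAP 4.1 and 4.2) use response, progression, death and subsequent-therapy dates. None of them uses the delay categories.

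**The case for a change.** The best case for a change is that 6 weeks is the only upper timing limit in the documents, that it stands in the same paragraph as the bins, and that the planned table cannot in general show how many gaps exceeded it. The programmable on-study deviations in SAP 7.2.2 name only concurrent antineoplastic therapy, so no programmed check supplies that count. Splitting the third bin at 28 days of delay would need one line of text and no new data. It can be added that Protocol 4.3.4 speaks of a delay over 6 weeks without saying from when.

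The arithmetic in this case stands, as does the point that off-grid restarts can put over-limit gaps in the third bin. The rest is weaker:

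- The scale is stated immediately before the bins. A reader goes wrong only by setting that definition aside.
- The SAP does not say that the top bin measures breaches of the limit. The shared number makes such a link plausible but does not establish it.
- A count of gaps over 6 weeks would not be a count of deviations, because Protocol 4.3.5 allows some of them.
- Protocol 4.3.4 refers to 4.3.5, which counts from the previous dose, as does 4.3; 3.1 counts between doses. The starting point is therefore supplied.
- The individual gaps can be worked out from the by-subject dosing listing in SAP 7.4.1. SAP 7.2.2 sends non-programmable relevant deviations to separate listings.

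**Conclusion.** No change is needed. The top cut lies 14 days beyond the limit when both are put on one scale, and the bin below it can hold gaps on both sides of 42 days. That is a choice of descriptive bins, not a miscalculation: the table would be correct under its own printed definition. Finer bins would be a harmless option for whoever programs the table, but they would not alter power, bias, any safety action or any conclusion of the trial. An analyst who wants gaps over 42 days can derive them from the listed dosing records.

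This rests on reading the duration of the previous cycle as the dose-to-dose gap, and on the delay bins feeding only the exposure summary, as they do in the SAP text. The Data Presentation Plan, which holds the table layouts, is not among the documents. How many patients had gaps of 43 to 55 days is unknown, but the conclusion does not depend on that number.
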